However, the role of PCI in ES-SCLC patients who have a good response to initial systemic therapy remains unclear. To date, there have been two randomized multicenter trials which evaluated PCI in ES-SCLC. An EORTC phase III trial by Slotman et al., randomized ES-SCLC patients with a response to chemotherapy to either PCI or observation. The primary end point for this study was symptomatic brain metastases. Of note, intracranial screening by MRI was not utilized prior to PCI. When compared to observation, PCI was associated with a lower risk of symptomatic brain metastases (hazard ratio [HR], 0.27; 95% confidence interval [CI], 0.16 to 0.44; $P < 0.001$), higher median disease-free survival (14.7 weeks vs 12.0 weeks), and higher median overall survival (6.7 months vs 5.4 months). The cumulative risk of brain metastases within 1 year was 14.6% in the irradiation group (95% CI, 8.3 to 20.9) vs 40.4% in the control group (95% CI, 32.1 to 48.6), and the 1-year survival rate was 27.1% (95% CI, 19.4 to 35.5) in the irradiation group vs 13.3% (95% CI, 8.1 to 19.9) in the control group [6].

Another phase III trial was performed in Japan, in which ES-SCLC patients with some response to initial chemotherapy were randomized to either PCI or observation. Unlike the EORTC trial, this trial required MRI screening prior to randomization. Preliminary interim analysis, presented at the American Society of Clinical Oncology annual meeting in 2014, demonstrated a trend towards worse overall survival with PCI (10.1 months vs 15.1 months, HR 1.38; 95% CI, 0.95 to 2.01; stratified log-rank test, $p = 0.091$). Compared to observation, PCI significantly reduced the risk of brain metastases (32.4% vs 58.0% at 12 months; Gray's test, $p < 0.001$) and had comparable PFS (median, 2.2 vs 2.4 months; HR 1.12; 95% CI, 0.82 to 1.54) [7].

Both the EORTC and Japanese trials confirm the impact of PCI on reducing the incidence of brain metastases in ES-SCLC patients. However, these trials provide conflicting data on whether PCI provides a survival benefit. Moreover, PCI adversely affects short term quality of life with side effects such as fatigue and hair loss [6]. In addition, there is concern for long-term radiation-induced neurological morbidity [8], [9]. As treatment for ES-SCLC becomes more successful, efforts to minimize neurotoxicity from PCI will be of paramount importance.

b) Tumor Treating Fields (TTFields) Overview

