 - c. History of cerebrovascular accident (CVA) within 6 months prior to start of study treatment
 - d. Active infection or serious underlying medical condition that would impair the ability of the patient to received protocol therapy.
 - e. History of any psychiatric condition that might impair patient's ability to understand or comply with the requirements of the study or to provide consent.
4. Active implantable electronic medical devices in the brain; a skull defect, a shunt, or bullet fragments
 5. Known allergies to medical adhesives or hydrogel
 6. Unable to operate the NovoTTF-200A device independently or with the help of a caregiver
 7. If a female, currently pregnant, breastfeeding, or unwilling to avoid pregnancy while on study treatment.
 8. Concurrent brain directed therapy (beyond NovoTTF-200A as per protocol)
 9. Prior clinical trial participation with brain directed therapy
 10. Concurrent treatment clinical trials

4. Criteria for Removal from Study Therapy

Criteria for removal from study therapy include:

1. Patient request – The patient may withdraw from the study at any time.
2. Lack of compliance – The Sponsor or investigator may remove a patient from the study for lack of compliance to the study protocol.
3. Intolerable toxicity - Patients may be removed from study treatment for intolerable adverse events attributable to the device. Any serious adverse event deemed life threatening by the treating physician that is definitely related to the study device will be cause for immediate cessation of treatment.
4. Intracranial failure – As defined in section 9(a) of the protocol
5. Death

5. Enrollment Plan

a) Start Date of Enrollment

Enrollment of the first patient is expected during the second quarter of 2017.-

b) Total Expected Duration of the Clinical Investigation

The study is expected to last for 36 months.

c) Expected Duration of Each Subject's Participation

Subject participation in the trial is anticipated to be 10-15 months.

d) Number of Subjects Required to be Included in the Clinical Investigation

A total of 25 patients will be accrued for this study at up to three institutions. Any patients deemed screen failures may be replaced with a new patient.

e) Estimated Time Needed to Select this Number (i.e., Enrollment Period).

It is assumed that the accrual will take place over 24 months.

Enrollment Procedures

Guidelines for VICC and Participating Institutions

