7. PATIENT EVALUATIONS AND FOLLOW UP PLAN

A table of the study procedure calendar for this study is provided in **Appendix C**.

a) Pre-treatment Evaluation (Baseline)

The following will be performed within 21 days prior to registration (start of study treatment with the NovoTTF-200A System):

1. Verify informed consent is signed
2. A high resolution, isovolumetric T1-weighted post-gadolinium MRI of the brain using a 3T MR scanner. **Treatment with the NovoTTF-200A System is to begin no later than 21 days after the baseline MRI.** Additional parameters include:
 - a) FOV: 256 mm x 256 mm

- b) Matrix: 256x256
- c) Slice thickness: 1 mm
- d) Full brain coverage

The same slice thickness and contrast material type & dose should be maintained throughout the entire study. The NovoTTF-200A System and all components including the transducer arrays must be removed and cannot be brought into the MR environment.

- 3. Medical history
- 4. Concomitant medications
- 5. Karnofsky Performance Status (KPS) score recording
- 6. Physical examination and vital signs
- 7. Neurological examination
- 8. Neurocognitive testing: Hopkins Verbal Learning Test (HVLT-R) for free recall, delayed recall and delayed recognition, Controlled Oral Word Association Test (COWAT); and Trail Making Tests (TMT) Parts A and B
- 9. Quality of Life questionnaire (EORTC QLQ C30 with BN20 addendum)
- 10. Serum Pregnancy test (if applicable) within 14 days
- 11. Complete blood count including differential
- 12. Serum chemistry panel, including:
 - 1. BUN, Creatinine
 - 2. Sodium, Potassium
 - 3. ALT, AST, Bilirubin
- 13. Coagulation tests (PT, PTT)

b) Follow-up until Intracranial Failure

Once every 8 weeks until intracranial failure the following examinations will be performed:

- 1. Physical examination and vital signs
- 2. KPS score recording
- 3. Neurological examination
- 4. Complete blood count including differential
- 5. Serum chemistry panel, including:
 - 1. BUN, Creatinine
 - 2. Sodium, Potassium
 - 3. ALT, AST, Bilirubin
- 6. Coagulation tests (PT, PTT) as clinically indicated
- 7. Adverse event collection and recording
- 8. Concomitant medication recording
- 9. A high resolution, isovolumetric T1-weighted post-gadolinium MRI of the brain using a 3T MR scanner. Additional parameters include:
 - a) FOV: 256 mm x 256 mm
 - b) Matrix: 256x256
 - c) Slice thickness: 1 mm
 - d) Full brain coverage

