3. COWAT

Once every 8 weeks, for one year or until intracranial failure (whichever comes first) the following Quality of Life questionnaires will be performed:

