c) Statistical Analysis – Primary Endpoint: Since this is a feasibility study, we will not attempt a strict control of multiplicity in analyses of the primary and secondary endpoints. Proportion of patients continuing TTF will be estimated using Wilson’s method and a one-sided 95% confidence interval will be reported. We will also summarize this measure for those who had PR and CR separately.

d) Statistical Analysis – Secondary Endpoints

Secondary endpoints for statistical testing: Time to intracranial failure with death as a competing risk will be estimated using cumulative incidence function (CIF) and reported with a one-sided 95% confidence interval. Rate of intracranial failure at a given time will be estimated using the CIF. Overall survival will be estimated using the Kaplan-Meier method. Other time-to-events data (with or without competing risks) will be analyzed similarly. Quality of life will be treated as a continuous endpoint; its mean will be estimated and reported with a 95% confidence interval. Toxicity (CTCAE 0-4) will be tabulated.

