Appendix B: Neurocognitive Function

According to Meyers and Brown (Meyers CA 2006), for a neurocognitive test battery to be useful in clinical research it should fulfill the following 6 criteria:

- a) It should be brief in order to reduce patient and clinical burden.
- b) It should have alternate forms of the tests in order to reduce practice effects and therefore allow for repeated test administration.
- c) It should have good psychometric properties such as validity, reliability, and population norms so that true changes in NCF above fluctuations due to situational factors can be detected.
- d) It should be sensitive to changes in cognitive function.
- e) It should be highly standardized and easy to administer so that no specialized psychological training is necessary in order to be able to administer the test battery.
- f) Most patients should be able to complete the neurocognitive tests, even patients with significant neurocognitive problems, in order to reduce the likelihood of selection bias.

See Statistical Considerations chapter for further information regarding the evaluation of neurocognitive endpoints

Test Battery for Neurocognitive Function

Neurocognitive Parameter Measured	Test	Time to Administer (Minutes)
Auditory/verbal learning and memory	Hopkins Verbal Learning Test-Revised	5
Visual-Motor Scanning Speed	Trail Making Test Part A	5
Executive Function	Trail Making Test Part B	5
Verbal Fluency	Controlled Oral Word Association Test	5
	Total Time	20

Prior to initiation of TTFs, all patients will undergo baseline neurocognitive testing using these neurocognitive instruments. At that time, history regarding level of education reached will also be obtained. After completion of therapy, all patients will undergo this neurocognitive test battery, conducted by trained and certified nurses or clinical research associates, every 8 weeks until death or until one year after therapy, whichever comes first. In the analysis of neurocognitive decline, each patient will serve as his/her own control, as decline for each neurocognitive test at each follow-up time point will be compared to baseline.

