Appendix C: Study Calendar

	T=(-21)-0 Days (Baseline)	T=0 days (Registration to Treatment)	T= 0 to 21 days (Registration to Treatment to 21)	T=every 8 weeks until intracranial failure (Follow-Up) (±7days)	T= 8 weeks from treatment termination (±7days)	T= every 4 weeks from treatment discontinuation (±7 days)
Signed ICF	X					
MRI of brain ¹	X			X	X	
Medical history	X					
Performance Status (KPS score)	X			X	X	
Physical examination ²	X			X	X	
Neurological examination	X			X	X	
Complete blood count including differential	X			X	X	
Serum chemistry panel ³	X			X	X	
Neurocognitive Testing ⁴	X			X		
Quality of Life Questionnaire ⁴	X			X		
Serum pregnancy test ⁵	X					
Blood coagulation test ⁶	X					
Registration to treatment (Start of use of NovoTTF-200A)		X				
Adverse event collection and recording ⁷		X	X	X	X	
Concomitant medication recording	X	X	X	X	X	
Device compliance assessment				X		
Telephone follow-up for survival						X

1. A high resolution, isovolumetric T1-weighted post-gadolinium MRI of the brain using a 3T MR scanner. **Treatment with the NovoTTF-200A System is to begin within 21 days after this baseline MRI.** Additional parameters include:

- FOV: 256 mm x 256 mm
- Matrix: 256x256
- Slice thickness: 1 mm
- Full brain coverage

The same slice thickness should be maintained throughout the study. The NovoTTF-200A System and all components including the transducer arrays must be removed and cannot be brought into the MR environment.

2. Vital signs are included as part of the physical exam
3. Serum chemistry panel includes: BUN, Creatinine, Sodium, Potassium, ALT, AST, Bilirubin
4. Neurocognitive Testing and QOL questionnaire will be performed for one year or until second cerebral progression (whichever comes first)
5. If applicable and within 14 days
6. Coagulation tests include PT, PTT and will be performed as part of the follow up procedures only if clinically indicated
7. Reporting period will begin immediately following registration to treatment (start of use of NovoTTF-200A) and ends at the conclusion of 8 weeks following treatment termination

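### Quality of life is analysed only as a mean with a 95% CI: the baseline score goes unused and loss of patients to death or intracranial failure is not addressed, so later means can look better than the cohort

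*Combined protocol and SAP*

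**What the plan says.** Section 9(d) covers quality of life in one sentence: "Quality of life will be treated as a continuous endpoint; its mean will be estimated and reported with a 95% confidence interval". Sections 6 and 9(a) add only the name of the instrument. None of these places gives a scale, an analysis visit, a comparison with baseline, or a rule for missing forms or death.

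The data collection is richer than the analysis. Section 7(a) lists "Quality of Life questionnaire (EORTC QLQ C30 with BN20 addendum") among the pre-treatment evaluations. Section 7(b) sets the follow-up: "Once every 8 weeks, for one year or until intracranial failure (whichever comes first) the following Quality of Life questionnaires will be performed". The visit 8 weeks after treatment termination, in Section 7(c) and Appendix C, has no quality-of-life form.

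Two other places matter:

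- Footnote 4 of the study calendar in Appendix C gives a different end point for the forms: "Neurocognitive Testing and QOL questionnaire will be performed for one year or until second cerebral progression (whichever comes first").
- Appendix B plans a within-patient comparison, but for the neurocognitive tests only: "each patient will serve as his/her own control, as decline for each neurocognitive test at each follow-up time point will be compared to baseline". Nothing extends this to quality of life.

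**The concern.** Patients leave the quality-of-life data through death and intracranial failure, the events that the study follows. If patients with poorer quality of life die or fail sooner, those who still answer at month 6 or 12 were better off at the start. Their mean then mixes who is left with how anyone has changed, and a stated analysis that ignores baseline cannot separate the two.

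This matters because Section 3(e) gives the harm of PCI to quality of life as a main reason for seeking an alternative, and Section 9(b) says that the pilot is meant to inform planning of the next phase. A mean among survivors that looks stable could be read as evidence that the device spares quality of life. The end of Section 7 states that nothing foreseeable may compromise interpretation, so this attrition is not covered there either.

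**Working it through.** The plan gives no figure for quality of life, so there is none to reproduce. The check asks how many patients could still be answering at 12 months, and how far a plain mean could move if no patient changed.

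**Inputs from the documents.** Sample size: "A total of 25 patients will be accrued for this study at up to three institutions" (Section 6). The trials cited in Section 3(a) give:

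- EORTC trial: "the 1-year survival rate was 27.1% (95% CI, 19.4 to 35.5) in the irradiation group vs 13.3"% in the control group; 1-year brain metastases 14.6% (PCI) and 40.4% (control).
- Japanese trial: 12-month brain metastases 32.4% (PCI) and 58.0% (observation); median survival 10.1 and 15.1 months.

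**Step 1. Ceiling on patients still giving forms at 12 months.** Under Section 7(b) a patient must be alive and free of intracranial failure, so the share cannot exceed the smaller of 1-year survival and 1 − brain-metastasis incidence. Where only a median is given, exponential survival is assumed.

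| Cited group | Survival | 1 − brain metastases | Ceiling | Of 25 |
|---|---|---|---|---|
| EORTC control | 13.3% | 59.6% | 13.3% | 3.3 |
| EORTC PCI | 27.1% | 85.4% | 27.1% | 6.8 |
| Japanese observation | 0.5^(12/15.1) = 57.6% | 42.0% | 42.0% | 10.5 |
| Japanese PCI | 0.5^(12/10.1) = 43.9% | 67.6% | 43.9% | 11.0 |

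The range is about 3 to 11 of 25. If the calendar's rule applied instead, a first failure would not end the forms and survival alone would set the ceiling. Only the Japanese observation row changes, to 57.6%, or 14.4 of 25.

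**Step 2. Shift of the plain mean if nobody changes.** Assumptions not in the documents: scores are normal with SD s = 20 points (range 15 to 25), higher is better, and r is the correlation between the score and time to death or failure (range 0 to 0.5). With share q still observed, the mean of those observed exceeds the cohort mean by

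shift = r × s × φ(z) / q, where z is the standard normal quantile at 1 − q.

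The factor φ(z)/q is 0.3909/0.42 = 0.931, 0.3313/0.271 = 1.222 and 0.2149/0.133 = 1.616. At s = 20:

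| r | q = 42% | q = 27.1% | q = 13.3% |
|---|---|---|---|
| 0 | 0 | 0 | 0 |
| 0.1 | +1.9 | +2.4 | +3.2 |
| 0.3 | +5.6 | +7.3 | +9.7 |
| 0.5 | +9.3 | +12.2 | +16.2 |

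For r = 0.3, SDs from 15 to 25 widen the range to +4.2 (15 × 0.3 × 0.931) through +12.1 (25 × 0.3 × 1.616). At q = 57.6% the factor is 0.680, so the shift at s = 20 is 0.3 × 20 × 0.680 = +4.1.

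**Step 3. True decline.** Take r = 0.3 and s = 20, and let every patient fall by the same amount. A 10-point fall shows as −10 + 5.6 = −4.4, −10 + 7.3 = −2.7 and −10 + 9.7 = −0.3. A 5-point fall shows as +0.6, +2.3 and +4.7. The plain mean understates decline in every case, but whether it rises depends on the size of the decline.

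**Step 4. What paired change achieves.** If dropout tracks only the baseline score, change from baseline among those observed is unbiased: 0 in Step 2, −10 or −5 in Step 3. If worsening itself also drives dropout, with correlation 0.3 and an assumed SD of individual change of 10, the remaining bias is 0.3 × 10 × (0.931, 1.222, 1.616) = +2.8, +3.7 and +4.8 points.

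**The case against.** A reader might infer that the quality-of-life result will drift upward as sicker patients drop out. The documents do not support that. The shift is zero if quality of life is unrelated to death or failure, the mean can still fall under true decline (Step 3), and on a scale where higher is worse the sign reverses. The plan names no scale or direction.

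Nor does the plan choose an unadjusted follow-up mean set against the baseline mean of all 25. It says only that a mean will be estimated. The fault is an analysis that ignores baseline and leaves the rest open, not a declared comparison of that kind.

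It would also be selective to cite EORTC survival alone and speak of 3 to 7 patients. Section 3(a) notes that the EORTC trial did not screen by MRI before PCI, whereas the Japanese trial did. This study excludes brain metastases on MRI, and the Japanese figures give about 10 to 11. The calendar footnote, if it governs, would keep patients with a first failure in the data.

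Finally, quality of life is the eighth of nine secondary objectives in a 25-patient single-arm pilot, and Section 3(e) ties the move to phase 2 to safety and tolerability. All of this stands, and it limits the strength and severity of the point. It does not supply the missing analysis: at least 10 of 25 patients, even on the most favourable figure above, would be gone by 12 months, and the baseline form would still be unused.

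**Conclusion.** The point holds as a gap in the stated analysis that permits a misleading summary. Later means would come from a selected subset, at most about 3 to 11 of 25 at 12 months under Section 7(b), and could look better than the cohort or understate decline. The counts assume that this study's patients resemble those in the cited trials; one of them also assumes exponential survival.

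The size of the distortion cannot be read from the documents. It is 0 points at correlation 0, and +5.6 to +9.7 points at correlation 0.3 with an SD of 20 and no true change; both inputs are assumptions. The primary endpoint and the sample size are unaffected. This is a cheap improvement, not a fault that threatens the study.

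**What to change.** Replace the sentence in Section 9(d) with:

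> For each scale, the mean within-patient change from baseline will be reported at each 8-weekly visit with a 95% CI, among patients with both forms, alongside the baseline mean of those same patients and the numbers alive, free of intracranial failure and completing the form. Results will be described as quality of life while alive and under assessment.

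Name the scales and their direction, and record reasons for missing forms. Reconcile Section 7(b), which ends the forms at intracranial failure, with footnote 4 of Appendix C, which ends them at second cerebral progression.

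A mixed model may be added as a sensitivity analysis, but not as the main one. Under missing at random it estimates scores as if lost patients had continued, which is not quality of life while alive and under assessment. An unstructured covariance over six follow-up visits needs 6 × 7 / 2 = 21 parameters per scale, too many for 25 patients.

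The cost is SAP wording and slightly more analysis, on data already collected. Two limits remain: the residual bias in Step 4 if worsening drives dropout, and low precision late in follow-up. With 10 patients and an SD of 20, the 95% CI half-width for a plain mean is 2.262 × 20/√10 = 14.3 points. With equal variances the SD of change is 20 × √(2(1 − ρ)), where ρ is the baseline to follow-up correlation. At an assumed ρ of 0.7 the half-width for paired change is 11.1 points; paired change is the more precise only when ρ exceeds 0.5.

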- Time to neurocognitive failure, as measured by cognitive decline on a battery of tests: HVLT-R free recall, delayed recall, and delayed recognition; COWAT; and TMT Parts A and B.
- Neurocognitive failure-free survival, defined from the date of starting NovoTTF-200A to neurocognitive failure (as measured by HVLT-R free recall, delayed recall, and delayed recognition; COWAT; and TMT Parts A and B) or death (whichever occurs first), censored at the last neurocognitive assessment on which the patient was reported alive without neurocognitive failure.
- Quality of Life using the EORTC QLQ C30 with BN20 addendum.
- Toxicity during NovoTTF-200A treatment based on incidence and severity of treatment emergent adverse events as evaluated using the CTCAE version 5.0 (**Appendix D**).

The above battery of neurocognitive instruments has been selected based on accepted standardization and psychometric principles, published normative data relative to routine demographics, relevance to general neurocognitive status, minimal practice effects, and brevity of the overall battery. Additionally, similar variations of this neurocognitive testing battery have been utilized in multiple cooperative group trials including RTOG 0212, RTOG 0214, RTOG 0424, RTOG 0525, RTOG 0933, ACOSOG Z0933,

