All adverse events will be captured on a centralized electronic case report form called ON-line Clinical Oncology Research Environment = Oncore

The following will be recorded:

a) Grading of an Adverse Event

The descriptions and grading scales found in the revised NCI Common Toxicity Criteria (CTC) version 5.0 will be utilized for assessing severity of adverse events. If the toxicity is not characterized adequately by the NCI toxicity scale, the investigator will use the adjectives MILD, MODERATE, SEVERE to describe the maximum intensity of the adverse event. For purposes of consistency, these intensity grades are defined as follows:

MILD	Grade 1	Mild; asymptomatic or mild symptoms; clinical or diagnostic observations only; intervention not indicated.
MODERATE	Grade 2	Moderate; minimal, local or noninvasive intervention indicated; limiting age-appropriate instrumental Activities of Daily Living (ADL)
SEVERE	Grade 3	Severe or medically significant but not immediately life-threatening; hospitalization or prolongation of hospitalization indicated; disabling; limiting self care ADL
POTENTIALLY LIFE-THREATENING	Grade 4	Life-threatening consequences; urgent intervention indicated.
DEATH	Grade 5	Death related to AE.

Modified Grading for NovoTTF-200A-Related Skin Adverse Events:

NovoTTF-200A -Related Skin Adverse Events
Grade 1 – Asymptomatic or mild symptoms AND 1. No intervention required OR only topical treatment intervention indicated 2. Treatment interruption of less than 3 days may be required.
Grade 2 – Moderate symptoms AND Systemic therapy required OR event is requiring interruption of NovoTTF-200A for more than 3 days.
Grade 3 – Severe or medically significant but not immediately life threatening AND hospitalization OR prolongation of existing hospitalization indicated

Grade 4 – Life threatening consequences AND urgent intervention indicated
--

Vanderbilt University Medical Center will be responsible for the classification of adverse events and ongoing safety evaluation of the clinical investigation.

Safety evaluation and reporting will be managed through the following actions:

1. Review the investigator's assessment of all **serious adverse events** and determine and document in writing their relationship to the investigational device;
2. Review all **device deficiencies** and determine and document in writing whether they could have led to a serious adverse device effect;

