A USADE is any serious adverse device effect whose nature, incidence, severity or outcome has not been identified in protocol Section 16.1a, Possible Adverse Events. Anticipated SADEs are effects whose nature, incidence, severity or outcome has been previously identified in protocol Section 16.1a, Possible Adverse Events. Any potential USADEs will be reported to the study monitor and local IRB within 10 days of the investigator learning of the event. The Sponsor will investigate and determine if the events are USADEs. Expedited reporting for FDA submission and reporting to other IRBs is to follow within 10 working days after first learning of the event by the Sponsor or their representative. If more than one USADE is observed in study patients, this will result in stopping of patient enrollment until further assessment by the data safety monitoring committee.

f) Reportable Events

For the purpose of this guidance and based on the definitions above, the following events are considered reportable events in accordance with FDA reporting requirements:

- any SAE,
- any Investigational Medical Device Deficiency that might have led to a SAE if a) suitable action had not been taken or b) intervention had not been made or c) if circumstances had been less fortunate,
- new findings/updates in relation to already reported events,
- USADEs

On this study:

- 1) Hospitalization duration of less than 24 hours is not considered to be a serious adverse event.
- 2) Death due to the primary disease (small cell lung cancer) need not be reported as an SAE. These SAEs will be captured in the CRFs as described for regular AEs.

Reportable events will be reported by the Sponsor or their designee to the appropriate regulatory authorities.

g) Reporting Timelines

Any SAE or USADE which indicates an imminent risk of death, serious injury, or serious illness and that requires prompt remedial action for other patients/subjects, users or other persons or a new finding to it will be reported immediately, but not later than 2 calendar days after awareness by Sponsor of a new reportable event or of new information in relation with an already reported event.

Any other reportable events or a new finding/updates must be reported immediately, but not later than 7 calendar days following the date of awareness by the Sponsor of the new reportable event or of new information in relation with an already reported event.

h) Determination of Causality of Adverse Events

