The adverse event reporting period will begin immediately following registration to treatment (start of use of the NovoTTF-200A device). Adverse events will be collected for 8 weeks following treatment termination. All adverse events that occur in trial patients during the adverse event reporting period specified in the protocol must be reported on the eCRFs, whether or not the event is considered study treatment-related. In addition, any known untoward event that occurs beyond the adverse event reporting period that the investigator assesses as possibly related to the investigational medication/product should also be reported as an adverse event.

k) Follow-up of Unresolved Adverse Events

All adverse events should be followed until they are resolved or the investigator assesses them as chronic or stable or the patient's participation in the trial ends. In addition, all serious adverse events and those non-serious events assessed by the investigator as probably related to the investigational medication/product should continue to be followed even after the patient's participation in the trial is over. Such events should be followed until they resolve or until the investigator assesses them as "chronic" or "stable." Resolution of such events is to be documented on the appropriate CRF.

l) Serious Adverse Events

All serious adverse events, regardless of causality to the study treatment, will be reported to the Principal Investigator and/or the Study Coordinator at each institution, and also to the Coordinating Center.

All serious adverse events must be reported to the Coordinating Center within 24 hours of the investigator becoming aware of the event. Events should be reported using the Vanderbilt SAE form.

The Vanderbilt SAE form must be fully completed and emailed, faxed, or scanned to:

ATTN: VICC CTSR Personnel
EMAIL: [contact]
[contact]

If SAE documents are faxed, the Coordinating Center must be notified via email as well. Follow-up information must also be reported within 24 hours of receipt of the information by the investigator.

If SAE documents are faxed, the Coordinating Center must be notified via email. Follow-up information must also be reported within 24 hours of receipt of the information by the investigator.

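### The only planned safety table stops at CTCAE grade 4, so it has no row for the fatal adverse events that the protocol grades 5.

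*Combined protocol and SAP*

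**What the plan says.** Section 9(d), on the secondary endpoints, gives the whole of the safety analysis in one sentence: "Toxicity (CTCAE 0-4) will be tabulated".

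The endpoint it serves is set out in Section 9(a), and in the same terms in Section 6.1(b): "Toxicity during NovoTTF-200A treatment based on incidence and severity of treatment emergent adverse events as evaluated using the CTCAE version 5.0". Neither place caps the grade.

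Section 16.2(a) sets the scale: "The descriptions and grading scales found in the revised NCI Common Toxicity Criteria (CTC) version 5.0 will be utilized". Its severity table runs from grade 1 to grade 5, and grade 5 is "Death related to AE".

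On data capture, Section 16.2(j) states: "All adverse events that occur in trial patients during the adverse event reporting period specified in the protocol must be reported on the eCRFs". This applies whether or not the event is considered related to treatment. Section 16.2(f) makes one exception to SAE reporting: "Death due to the primary disease (small cell lung cancer) need not be reported as an SAE". It then adds: "These SAEs will be captured in the CRFs as described for regular AEs".

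**The concern.** The grade range in the analysis sentence is narrower than both the endpoint and the scale used to collect the data. The grade left out is the most severe one. An analyst who follows Section 9(d) to the letter produces a table in which a death related to an adverse event has no place.

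This matters because Section 3(e) makes consideration of a phase 2 study conditional on safety and tolerability. With 25 patients and one arm, the adverse event table is the main summary on which that judgement would rest. If the range is left until a death has occurred, how to present that death becomes an unplanned decision made with the data in view.

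**Working it through.** **1. Grade ranges side by side.**

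| Place | Range |
|---|---|
| Safety endpoint, Sections 6.1(b) and 9(a) | CTCAE 5.0, no cap |
| Severity scale, Section 16.2(a) | Grades 1 to 5 |
| Planned table, Section 9(d) | Grades 0 to 4 |

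Exactly one defined grade, grade 5, is missing from the table. Section 16.2(a) also has a modified scale that ends at grade 4, but it covers only device-related skin events and cannot account for a cap on the whole table.

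**2. Does another planned analysis report these events?**

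- Overall survival, Section 9(a): counts death from any cause, without attribution to an adverse event or the device.
- Primary endpoint, Section 9(a): death is not an event, and patients without intracranial failure are censored at death.
- SAE reporting (Section 16.2) and quarterly review by the data monitoring committee (Section 8): oversight during the trial, not an analysis of the endpoint.
- A listing of deaths by cause or relatedness: none is planned.

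**3. Check of the interval method.** The plan's only design figures are the intervals in Section 9(b) for n = 25. The Wilson interval is

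[p + z²/(2n) ± z·√(p(1−p)/n + z²/(4n²))] / (1 + z²/n), with z = 1.96.

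For 10, 15, 18 and 20 patients of 25 it gives 23.4% to 59.3%, 40.7% to 76.6%, 52.4% to 85.7% and 60.9% to 91.1%. All match the plan's table after rounding, so the same formula is used below.

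**4. Scale of one omitted event.** Take p = 1/25 = 0.04.

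- z²/n = 0.1537, so the denominator is 1.1537.
- Centre: (0.04 + 0.0768)/1.1537 = 0.1013.
- Half-width: 1.96 × √(0.001536 + 0.001537)/1.1537 = 0.0942.
- Result: 4.0%, interval 0.7% to 19.5%.

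**5. How likely is at least one?** The documents give no fatal-event rate, so a range is assumed. The chance is 1 − (1 − r)^25.

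| Assumed rate r | Chance of at least one grade 5 event in 25 |
|---|---|
| 1% | 22% |
| 2% | 40% |
| 5% | 72% |
| 10% | 93% |

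**6. Disease deaths.** Deaths from small cell lung cancer should be expected during the study. The two randomized trials summarised in Section 3(a) report median survival between 5.4 and 15.1 months across their arms, and eligibility asks only for a life expectancy above 3 months. Section 16.2(f) sends these deaths to the CRF as ordinary adverse events. A grade 5 row added with no further rule could therefore mix them with deaths related to an adverse event.

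**The case against.** The strongest reply is that this is a drafting slip with no practical effect. The endpoint has no cap, so an analyst working from the endpoint definition would include grade 5. The range looks like shorthand in any case, since the severity table in Section 16.2(a) has no grade 0 either. If the table were built by worst grade per patient, a dropped death would show as a total below 25. Safety oversight does not depend on the table: adverse events leading to death are SAEs, they go to the coordinating center within 24 hours, and the monitoring committee reviews SAEs quarterly. Section 16.1(a) reports no serious events attributed to the device in the recurrent glioblastoma trial and expects none here.

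Much of this stands, and it limits the consequence to presentation. It does not remove the mismatch. The plan does not say that the table is by worst grade per patient, so the check on the total cannot be relied on. The endpoint covers treatment-emergent events whatever their cause, in patients who may also receive chest irradiation or systemic therapy, so the device's record elsewhere does not make a grade 5 event implausible. If the range is a slip, it is best corrected before analysis.

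A reader might infer three stronger things that the documents do not support:

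- **That a death would be recorded one grade too low.** Section 16.2(a) fixes grading. Section 9(d) governs only tabulation.
- **That the table would show 0 of 25 in its worst row, with an upper limit of 13.3%.** The arithmetic is right, but the row is empty only if there are also no grade 4 events, and the plan specifies no confidence interval for toxicity.
- **That fatal events would be lost from the trial.** They reach the eCRF and overall survival and, apart from disease deaths, SAE reporting and committee review.

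**Conclusion.** The point holds as an internal inconsistency in the analysis text that should be corrected. Read literally, Section 9(d) leaves out the most severe grade the protocol defines, and no other planned analysis reports fatal adverse events by event or by relationship to the device. The effect is confined to the reported safety result; data capture and oversight are intact.

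The 4.0% for a single event, with its wide interval, shows how much one omitted death would weigh in a study of this size. It assumes one such event and is not a forecast. The chances of 22% to 93% rest wholly on the assumed rates of 1% to 10%. The conclusion itself rests on none of these figures, only on comparing Sections 9(d), 9(a) and 16.2(a).

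**What to change.** In Section 9(d), change the tabulated range from CTCAE grades 0-4 to grades 0-5. Add a sentence stating that each grade 5 event will be listed with its recorded relationship to the device, and that deaths due to small cell lung cancer, as exempted in Section 16.2(f), will be shown separately from deaths related to an adverse event.

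The cost is one or two sentences in the plan. Grade and causality are already specified for recording in Sections 16.2(a) and 16.2(h), so no new data are needed. Sample size, visits and conduct do not change.
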